### 5.1.2.2 Statistical Methods

The hypotheses associated with the secondary immunogenicity objectives will be tested only if the primary objective is demonstrated, and then each of the secondary immunogenicity objectives will be evaluated sequentially following a fixed-sequence method as specified below (5) (6) (7).

This method allows to conclude on any of the hypothesis testing conducted at one-sided 0.025 nominal alpha without inflation of overall Type I error, provided the sequence specified hereafter is respected:

- **Secondary immunogenicity objective 1: Superiority in the 3-dose VRVg-2 group at D42**

Only if the primary objective is achieved at D42, the superiority of VRVg-2 group at D42 will be assessed on overall subjects in VRVg-2 group.

The null hypothesis will be rejected and the 1st secondary immunogenicity objective will be achieved if the observed proportion of subjects with an RVNA titer  $\geq 0.5$  IU/mL at D42 in VRVg-2 group is at least 99.0%, and the lower limit of the 95% CI of the proportion calculated using the exact binomial distribution (Clopper Pearson method) (1) is at least 97%.

- **Secondary immunogenicity objective 2: NI testing of 2-dose VRVg-2 at D28 versus 2-dose Verorab and Imovax Rabies at D28**

Only if the 1st secondary immunogenicity objective is achieved, based on the same statistical approach for the primary objective, the non-inferiority of VRVg-2 compared to each of the comparator vaccines will be tested at D28, in each age group (ie, in pediatric subjects and adult subjects, respectively), with the two-sided 95% CI of the difference of the 2 proportions at D28, calculated using Wilson score method without continuity correction (2).

The null hypothesis will be rejected if the lower limit of the two-sided 95% CI of the difference of the 2 proportions ( $P_{VRVg-2} - P_{control}$ ) is  $> -5\%$ .

The 2nd secondary immunogenicity objective of NI at D28 will be demonstrated if all null hypotheses are rejected.

- **Secondary immunogenicity objective 3: NI testing of 2-dose VRVg-2 at D28 versus 3-dose Imovax Rabies at D42**

Only if the 2nd secondary immunogenicity objective is achieved, based on the similar statistical approach for the primary objective, the non-inferiority of 2-dose VRVg-2 compared to 3-dose Imovax Rabies will be tested, in each age group (ie, in pediatric subjects and adult subjects, respectively), with the two-sided 95% CI of the difference of the 2 proportions, calculated using Wilson score method without continuity correction (2).

The null hypothesis will be rejected if the lower limit of the two-sided 95% CI of the difference of the 2 proportions ( $P_{VRVg-2 \text{ at D28}} - P_{\text{Imovax Rabies at D42}}$ ) is  $> -10\%$ .

The 3rd secondary immunogenicity objective will be demonstrated if all null hypotheses are rejected.

In addition, supplemental analysis will be performed based on NI margin of -5%, using the same statistical method.

- **Secondary immunogenicity objective 4: Superiority in the 2-dose VRVg-2 group at D28**

Only if the 3rd secondary immunogenicity objective is achieved, based on the same statistical approach for the 1st secondary immunogenicity objective, the superiority of VRVg-2 group at D28 will be assessed on overall subjects in VRVg-2 group.

The null hypothesis will be rejected and the 4th secondary immunogenicity objective will be achieved if the observed proportion of subjects with an RVNA titer  $\geq 0.5$  IU/mL at D28 in VRVg-2 group is at least 99%, and the lower limit of the 95% CI of the proportion calculated using the exact binomial distribution (Clopper Pearson method) (1) is at least 97%.

- **Secondary immunogenicity objective 5: NI testing of 2-dose Imovax Rabies at D28 versus 3-dose Imovax Rabies at D42**

Only if the 4th secondary objective is achieved, the 5th secondary immunogenicity objective will be assessed on overall subjects in Imovax Rabies group in Cohort 1 only, using the statistical methods mentioned below, based on NI margin of -10%.

In addition, supplemental analysis will be performed based on NI margin of -5%, using the same statistical method.

#### **Generalized Linear Model**

The null hypothesis will be rejected and 5th secondary immunogenicity objective will be achieved if the lower limit of the two-sided 95% CI of the difference of the 2 proportions ( $P_{\text{Imovax Rabies at D28}} - P_{\text{Imovax Rabies at D42}}$ ) is  $> -10\%$ , which will be calculated using a generalized linear model (GLM) for repeated measured data with categorical response under binomial distribution (link function=identity) (8).

All subjects in Imovax Rabies group in Cohort 1 (Group 3) with at least one available immunogenicity assessment at D28 or D42 will be included in the GLM. An example of SAS code is presented as below.

```
proc genmod data=immuno;
  class ID time_point;
  model response(event="1") = timepoint / dist=binomial link=identity;
  repeated subject=ID;
  lsmeans time_point / diff cl;
run;
```

where event="1" refers to an occurrence of RVNA titer  $\geq 0.5$  IU/mL at D28 or D42 in Imovax Rabies Group in Cohort 1 (Group 3), timepoints is the time point for repeated immunogenicity measures including D28 and D42, and ID is the unique subject identifier for each subject.

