#4	Overall (Pooled Pediatric and Adult Subjects in Pooled C1 and C2)	VRVg-2: 831	Sufficiency threshold: SC rate at D42 \geq 99.0%, with LL of 95%CI \geq 97.0%	98.9^b
#5	Overall (Pooled Pediatric and Adult Subjects in C1 only)	Imovax Rabies at D28: 168 Imovax Rabies at D42: 168	SC rate at D28: 96.5% SC rate at D42: 99.0% NI margin: -10%	90.0^c

a Power calculated using Farrington and Manning (FM) method.

b Power calculated using Binomial Exact method.

c Power calculated using simulation (10000 times, assuming correction coefficient [Rho]=0.5), based on general linear model (GLM) for repeated measured data with categorical response under binomial distribution (link function=identify).

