#### **MOVER Wilson score method**

In case GLM did not converge (e.g. if the seroconversion rate is 0% or 100% at D28 or D42 in Group 3 in Cohort 1), MOVER Wilson score method for paired binomial proportion (9) will be used to calculate the two-sided 95% CI of the difference between D28 and D42.

Only subjects with available immunogenicity data at both D28 and D42 will be included in the analysis using Mover Wilson score method as below.

The observed subjects with available immunogenicity data at both D28 and D42 can be summarized in a  $2 \times 2$  contingency table, as shown in [Table 5.2](#).

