**Table 5.7: Sample size and power estimation for primary and key secondary immunogenicity objectives**

Key Immunogenicity Objective	Age group	Evaluable N in the PPAS	Estimation/Margin	Power (%)
Primary Objective	Pediatric Subjects (Cohort[C] 1)	VRVg-2: 261 Verorab: 88	Seroconversion (SC) rate at D42: 99.0% NI margin: -5%	95.4 a
		VRVg-2: 261 Imovax Rabies: 88	Same as above	95.4 a
	Adult Subjects (C1)	VRVg-2: 243 Verorab: 81	Same as above	93.8 a
		VRVg-2: 243 Imovax Rabies: 81	Same as above	93.8 a

				Overall: 80.0a
Key Secondary Objectives				
#1	Overall (Pooled Pediatric and Adult Subjects in C1)	VRVg-2: 504	Sufficiency threshold: SC rate at D42 $\geq$ 99.0%, with lower limit (LL) of 95%CI $\geq$ 97.0%	86.3b
#2	Pediatric Subjects (C1)	VRVg-2: 261 Verorab: 88	SC rate at D28: 99.0% NI margin: -5%	95.4 a
		VRVg-2: 261 Imovax Rabies: 88	Same as above	95.4 a
	Adult Subjects (Pooled C1+C2)	VRVg-2: 570 Verorab: 190	SC rate at D28: 96.5% NI margin: -5%	93.8 a
		VRVg-2: 570 Imovax Rabies: 190	Same as above	93.8 a
Overall: 80.1a				
#3	Pediatric Subjects (C1)	VRVg-2 at D28: 261 Imovax Rabies at D42: 88	SC rate at D28: 99.0% SC rate at D42: 99.0% NI margin: -10%	>99.9 a
	Adult Subjects (D28 from Pooled C1+C2, D42 from C1)	VRVg-2 at D28 (Pooled Cohort 1+ Cohort 2): 570 Imovax Rabies at D42: 81	SC rate at D28: 96.5% SC rate at D42: 99.0%NI margin: -10%	>99.9 a
	Overall: >99.9a			
#4	Overall (Pooled Pediatric and Adult Subjects in Pooled C1 and C2)	VRVg-2: 831	Sufficiency threshold: SC rate at D42 $\geq$ 99.0%, with LL of 95%CI $\geq$ 97.0%	98.9b
#5	Overall (Pooled Pediatric and Adult Subjects in C1 only)	Imovax Rabies at D28: 168 Imovax Rabies at D42: 168	SC rate at D28: 96.5% SC rate at D42: 99.0% NI margin: -10%	90.0c

a Power calculated using Farrington and Manning (FM) method.

b Power calculated using Binomial Exact method.

c Power calculated using simulation (10000 times, assuming correction coefficient [Rho]=0.5), based on general linear model (GLM) for repeated measured data with categorical response under binomial distribution (link function=identify).

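### Objective 5's decision rule runs above its one-sided 2.5% level (4.1-4.5% at the plan's own D42 rate of 99%), and its stated power of 90.0% does not follow from the inputs beside it, which give 99.5%

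*SAP*

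**What the plan says.** SAP 5.1.2.2 tests objective 5 in the Cohort 1 Imovax Rabies group (Group 3, children and adults pooled). The null hypothesis is rejected if the lower limit of the two-sided 95% CI for the D28 minus D42 difference exceeds -10%, with the limit "calculated using a generalized linear model (GLM) for repeated measured data with categorical response under binomial distribution (link function=identity"). The GLM uses every Group 3 subject with a result at either time point.

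The fallback is conditional: "In case GLM did not converge (e.g. if the seroconversion rate is 0% or 100% at D28 or D42" in Group 3), the MOVER Wilson paired interval is computed on subjects with both results. Its formulas are written out in full.

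On error control, the opening of SAP 5.1.2.2 says that the fixed sequence "allows to conclude on any of the hypothesis testing conducted at one-sided 0.025 nominal alpha without inflation of overall Type I error", provided the order is kept. For objective 5 a "supplemental analysis will be performed based on NI margin of -5%, using the same statistical method" is also planned.

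On power, row #5 of SAP Table 5.7 lists "Imovax Rabies at D28: 168 Imovax Rabies at D42: 168", and the same row of Protocol Table 12.1 gives "SC rate at D28: 96.5% SC rate at D42: 99.0% NI margin: -10"%. Both tables, and the synopsis table, state 90.0%. Footnote c reads "Power calculated using simulation (10000 times, assuming correction coefficient [Rho]=0.5"), based on the GLM.

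**The concern.** A fixed sequence controls overall error only if each test in it holds its own level. The primary objective and objectives 2 and 3 use Wilson score limits, and objectives 1 and 4 use Clopper-Pearson. Objective 5 alone uses a Wald-type limit, although its expected rates are 96.5% and 99.0%, where Wald limits are known to be too short on the side that matters here. The claim at stake is that two Imovax Rabies doses are non-inferior to three.

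The power entry looked wrong for a separate reason. With 168 subjects measured twice, correlation 0.5 and a true difference of -2.5 points against a margin of -10, power should be far above 90%.

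**Working it through.** **Inputs.** N = 168 at each time point, D28 rate 96.5%, D42 rate 99.0%, Rho 0.5, margin -10% (SAP Table 5.7, row #5 and footnote c); level "one-sided 0.025 nominal alpha without inflation of overall Type I error" (SAP 5.1.2.2). Assumptions: all 168 subjects are complete pairs, and the fallback applies exactly when D28 or D42 is 0% or 100%.

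**Formulas.** Notation follows SAP Table 5.2, with d = (n12 - n21)/N.
- GLM limit: with two time points and complete pairs, d - 1.96 × √[(n12 + n21 - (n12 - n21)²/N)/N²]. This matched a GEE fit (identity link, robust standard error) on three test tables.
- MOVER Wilson limit: as written in the SAP.
- SAP rule: MOVER Wilson if either rate is 0% or 100%, otherwise the GLM limit.

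One table shows the gap. With n11 = 155, n12 = 0, n21 = 10, n22 = 3, d = -10/168 = -5.95 points and SE = √[(10 - 100/168)/168²] = 1.825 points. The GLM limit is -5.95 - 1.96 × 1.825 = -9.53, which passes. The MOVER Wilson limit is -10.68, which fails.

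**Step 1: the stated 90.0%.** Cell probabilities:
- both time points ≥ 0.5 IU/mL: 0.965 × 0.990 + 0.5 × √(0.965 × 0.035 × 0.990 × 0.010) = 0.95535 + 0.00914 = 0.96449
- D28 only: 0.965 - 0.96449 = 0.00051
- D42 only: 0.990 - 0.96449 = 0.02551
- neither: 0.00949

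Exact enumeration over all tables with N = 168 gives:

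| Power at -10% | GLM limit | SAP rule | MOVER throughout |
|---|---|---|---|
| Rho 0.5 (as stated) | 99.6% | 99.5% | 98.8% |
| Rho 0 | 98.3% | 97.7% | 95.3% |

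The 90.0% does not reproduce. Other readings were tried:
- Rho as a latent-normal correlation: 98.4%
- unpaired Farrington-Manning: 95.4%
- every non-convergent sample (18.5% of them) counted as a failure: 81.2%
- 84 pairs, i.e. 168 observations in total: 89.1%, but the row lists 168 at each time point

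The table itself is being read correctly: Farrington-Manning reproduces its 95.4% and 93.8% entries for the primary objective and objective 2. Row #5 also applies 96.5% at D28 to children and adults together, whereas rows #2 and #3 give children 99.0%. With 88 children at 99.0% and 168 - 88 = 80 adults at 96.5%, power exceeds 99.9%.

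**Step 2: one-sided error at the margin.** Set D28 = D42 - 10 points, N = 168, and take the range over all feasible non-negative correlations:

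| True D42 rate | SAP rule | MOVER throughout |
|---|---|---|
| 95% | 3.2-4.8% | 2.1-2.5% |
| 97% | 3.5-4.8% | 1.9-2.4% |
| 98% | 3.7-4.7% | 1.9-2.3% |
| 99% (plan's assumption) | 4.1-4.5% | 1.9-2.3% |
| 99.5% | 3.6-4.0% | 1.9-2.3% |
| 99.9% | 2.7-3.0% | 2.2-2.3% |
| 99.99% | 2.4% | 2.3% |

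The fallback rescues the level only when D42 is practically 100%. At 99% it is triggered in about 0.99^168 = 18.5% of trials.

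Rho 0.5 cannot hold at the null point 89%/99%, where the largest possible value is √(0.89 × 0.01/(0.11 × 0.99)) = 0.29.

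**Step 3: a mixed population.** If 88 children stay at 99% at both times and 80 adults fall by 21 points, the pooled drop is 80 × 21/168 = 10 points. By simulation the SAP rule then passes in 3.2-3.5% of trials, and MOVER throughout in 1.5-1.7%.

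**The case against.** The strongest reply has five parts.

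- **The SAP speaks of a nominal level within a multiplicity argument, not of exact size.** True, but the argument needs each test to hold that level, at least closely, and an actual 4.1-4.5% is not close to 2.5%.
- **Objective 5 must first be reached.** Objectives 1 and 4 each need an observed VRVg-2 rate of at least 99%. At a true rate of 99% they pass with probability 61% (n = 504) and 55% (n = 831), so the unconditional false-claim rate is about 0.55 × 4.5% = 2.5% or less. At the plan's own D28 rates objective 4 would almost never pass. This stands as a limit on scope. At a true VRVg-2 rate of 99.5%, however, each gate passes in about 96-97% of trials and protects almost nothing.
- **The size depends on scenarios the documents do not give.** This stands. Values near 4.8% need D42 rates below the planned 99% together with strong correlation. The mixed population, arguably the more realistic null, gives 3.2-3.5%. All of these exceed 2.5%.
- **Non-convergence could be more frequent than assumed.** The 0% or 100% case is only the SAP's example, and SAS was not run. More non-convergence would send more samples to MOVER Wilson and lower the error.
- **MOVER Wilson is conservative and drops subjects with one sample.** This is a real cost and is counted under the fix.

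On power, the simulation details are not given, so the source of 90.0% cannot be settled from the documents. None of the readings tried lands on it.

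**Conclusion.** Both parts hold. As specified, objective 5 is tested at about 4.1-4.5% one-sided under the plan's D42 assumption, 3.2-3.5% if adults alone carry the drop, and 2.7-4.8% over D42 rates of 95-99.9%. It meets 2.5% only when D42 is practically 100%. These figures rest on 168 complete pairs, non-negative correlation, and fallback exactly at 0% or 100%. They describe the test once it is reached.

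The power entry should read about 99.5% for the stated inputs and the SAP rule, not 90.0%.

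The consequences are limited. Objective 5 is last, concerns the comparator only, and the power figure is understated and did not set the sample size. It should still be corrected: the error-control statement is not true for this test, and a wrong figure stands in both documents.

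**What to change.** 1. In SAP 5.1.2.2 and Protocol 12.1.2.2 (and the synopsis), make the MOVER Wilson paired interval the deciding method for objective 5 in all cases. Keep the GLM as a supplementary analysis using all subjects with at least one result. No new formulas are needed.
2. Recompute row #5 in SAP Table 5.7, Protocol Table 12.1 and the synopsis table for the chosen method at -10%. State the D28 rate assumed for the pooled children and adults, and the number of pairs. If 90.0% came from other inputs, give them.

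Cost: wording only. Power at -10% falls from 99.5% to 98.8% at Rho 0.5, and from 97.7% to 95.3% at Rho 0. Subjects with only one of the two samples leave the deciding analysis. The supplemental -5% reading becomes harder to meet if it uses the same method: from 50% to 21% at the row #5 inputs, and from 84% to 64% with 88 children at 99% and 80 adults at 96.5% at D28. That reading does not decide the objective.

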#### **MOVER Wilson score method**

In case GLM did not converge (e.g. if the seroconversion rate is 0% or 100% at D28 or D42 in Group 3 in Cohort 1), MOVER Wilson score method for paired binomial proportion (9) will be used to calculate the two-sided 95% CI of the difference between D28 and D42.

Only subjects with available immunogenicity data at both D28 and D42 will be included in the analysis using Mover Wilson score method as below.

The observed subjects with available immunogenicity data at both D28 and D42 can be summarized in a  $2 \times 2$  contingency table, as shown in [Table 5.2](#).

**Table 5.2: The observed subjects with available RVNA titer assessments at both D28 and D42**

Time points		D42		
		RVNA titer $\geq 0.5$ IU/mL	RVNA titer $< 0.5$ IU/mL	Total
D28	RVNA titer $\geq 0.5$ IU/mL	$n_{11}$	$n_{12}$	$n_{1+}$
	RVNA titer $< 0.5$ IU/mL	$n_{21}$	$n_{22}$	$n_{2+}$
Total		$n_{+1}$	$n_{+2}$	$N$

where  $n_{11}$  corresponds to the number of subjects with an RVNA titer  $\geq 0.5$  IU/mL at both D28 and D42.  $n_{12}$  is the number of subjects with an RVNA titer  $\geq 0.5$  IU/mL at D28 and an RVNA titer  $< 0.5$  IU/mL at D42.  $n_{21}$  is the number of subjects with an RVNA titer  $< 0.5$  IU/mL at D28 and an RVNA titer  $\geq 0.5$  IU/mL at D42.  $n_{22}$  is the number of subjects with an RVNA titer  $< 0.5$  IU/mL at both D28 and D42.  $n_{1+}$  and  $n_{+1}$  are the numbers of subjects with an RVNA titer  $\geq 0.5$  IU/mL at D28 and D42, respectively.  $n_{2+}$  and  $n_{+2}$  are the numbers of subjects with an RVNA titer  $< 0.5$  IU/mL at D28 and D42, respectively.  $N$  is the total number of subjects with available immunogenicity data at both D28 and D42.

For paired data, let the difference of proportions of subjects with an RVNA titer  $\geq 0.5$  IU/mL between the 2 compared timepoints  $\hat{\theta} = p_1 - p_2$ , then  $L^* = \hat{\theta} - \nu$  and  $U^* = \hat{\theta} + \lambda$  are the lower and the upper limits of the CI, respectively, where:

$$\nu = \sqrt{(p_1 - l_1)^2 + (u_2 - p_2)^2 - 2\hat{\psi}(p_1 - l_1)(u_2 - p_2)}$$

$$\lambda = \sqrt{(u_1 - p_1)^2 + (p_2 - l_2)^2 - 2\hat{\psi}(u_1 - p_1)(p_2 - l_2)}$$

$l_1$  and  $u_1$  are calculated from the CI of the single proportion of subjects with an RVNA titer  $\geq 0.5$  IU/mL at D28 (ie,  $P_{\text{Imovax Rabies at D28}}$ ) given by:

$$(l_1, u_1) = \frac{2n_{1+} + Z_{0.025}^2 \pm Z_{0.025} \sqrt{Z_{0.025}^2 + 4n_{1+}(1 - \frac{n_{1+}}{N})}}{2(N + Z_{0.025}^2)}$$

$l_2$  and  $u_2$  are calculated from the CI of the single proportion of subjects with an RVNA titer  $\geq 0.5$  IU/mL at D42 (ie,  $P_{\text{Imovax Rabies at D42}}$ ) given by:

$$(l_2, u_2) = \frac{2n_{+1} + Z_{0.025}^2 \pm Z_{0.025} \sqrt{Z_{0.025}^2 + 4n_{+1}(1 - \frac{n_{+1}}{N})}}{2(N + Z_{0.025}^2)}$$

where  $Z_{0.025}$  is the upper 97.5th percentile of the standard normal distribution.

$\hat{\psi}$  is an estimate of the correlation coefficient between  $\hat{p}_1$  and  $\hat{p}_2$ .  $\hat{\psi}$  will be 0 if any of the marginal sums ( $n_{1+}$ ,  $n_{2+}$ ,  $n_{+1}$ ,  $n_{+2}$ ) is 0. Otherwise, let  $A = n_{11}n_{22} - n_{12}n_{21}$  and compute  $\hat{\psi}$  as

$$\hat{\psi} = \begin{cases} (A - N/2) / \sqrt{n_{1+}n_{2+}n_{+1}n_{+2}} & \text{if } A > N/2, \\ 0 & \text{if } 0 \leq A \leq N/2, \\ A / \sqrt{n_{1+}n_{2+}n_{+1}n_{+2}} & \text{if } A < 0. \end{cases}$$

- **Other secondary immunogenicity and safety objectives**

All other secondary endpoints will be described by age group and vaccine group using descriptive statistical methods without hypothesis testing, as follows.

***Immunogenicity endpoints***

A descriptive analysis of RVNA titers (IU/mL) will be performed by vaccine group and age group for the following statistics at each timepoint (D0 and D28 [for subjects in Cohort 1 and Cohort 2], D42 [for subjects in Cohort 1]; M12 and M12+D14 [for subjects in Booster Phase of Cohort 1]; M6, M12, M18, M24 up to M36, and M24 up to M36+D14 [for subjects in Immunogenicity Persistence and Booster Phase of Cohort 2]):

- Number of subjects with RVNA titer available
- Number and percentage of subjects with RVNA titer  $\geq 0.5$  IU/mL, and 95% CI of the proportion
- Number and percentage of subjects with RVNA titer  $\geq 0.2$  (LLOQ) IU/mL, and 95% CI of the proportion
- Number and percentage of subjects with complete or incomplete results at the starting dilution (1/5) of the RFFIT assay, and 95% CI of the proportion
  - Among the analysis population
  - Among the subset of subjects with a determined result (identical duplicate values, either Complete or Incomplete)
- GMTs and 95% CI of RVNA titers
- The GM of individual titer ratio (GMTR) between the post-vaccination time points and the baseline (D0) within each group, and 95% CI:
  - D28/D0
  - D42/D0
  - M6/D0
  - M12/D0
  - (M12+D14)/D0
  - M18/D0

- (M24 up to M36)/D0
- (M24 up to M36+D14)/D0
- The GMTR between the post-booster vaccination time point and the corresponding pre-booster vaccination time point within each group, and 95% CI:
  - (M12+D14)/M12
  - (M24 up to M36+D14)/ M24 up to M36
- Distribution of titers (minimum, Q1, median, Q3, maximum): based on Log10 transformation first and then antilog transformation.
- Log10 (Titer): mean and SD
- RCDC of RVNA titers

### *Safety endpoint*

The analysis will be descriptive using the Safety Analysis Set (SafAS) in the primary series and the Safety Analysis Set for booster (SafASB), for each vaccination group. The statistics presented on [Table 5.1](#) will be produced.

The safety analysis will report the occurrence of solicited reactions and the incidence of unsolicited AEs, including SAEs and AESIs, over the safety observation period by age group and vaccine group according to the vaccine received.

- Immediate unsolicited systemic AEs reported in the 30 minutes after each vaccination
- Solicited injection site reactions occurring within 7 days after each vaccination
- Solicited systemic reactions occurring within 7 days after each vaccination
- Unsolicited injection site AEs occurring within 28 days after each vaccination
- Unsolicited systemic AEs occurring between each vaccination and up to 28 days after the last vaccination
- SAEs and AESIs throughout the study (until 6 months after last vaccination for the primary vaccination series and throughout the entire study for the subset of subjects included in the booster phase)

In order to avoid any under-estimation of the incidences, the number of subjects with documented safety will be used as denominator of the frequencies.

- For solicited reactions, the denominator is the total number of subjects who have non-missing data for the particular category of reaction during the time period concerned.

**Note:** for solicited systemic reactions, if a reaction is ongoing at the time of the next vaccination, it will be treated differently depending on whether or not it has increased in intensity following the later vaccination.

- If it has not increased in intensity after the next vaccination, it is to be attributed to the earlier vaccination, and is counted as just a single occurrence in safety analysis. The time of onset is the first day of the first occurrence in the earlier vaccination.

- If it has increased in intensity after the next vaccination, it will be counted as 2 separate occurrences after each vaccination in safety analysis (the 2 occurrences will be attributed to the earlier vaccination and later vaccination, respectively). The date of the later vaccination will be considered as the end date for the first occurrence and the start date of the second occurrence, respectively.
- For unsolicited events, the denominator is the total number of subjects who were vaccinated at the dose analyzed (for the analyses after each dose) or the total number of subjects who were vaccinated at least one dose (for the analyses after any dose).

For safety parameters, 95% CIs of point estimates of proportion will be calculated using the exact binomial distribution (Clopper-Pearson method) for proportions [\(1\)](#).

